Department of Critical Care, Division of Anesthesiology and Critical Care,
The University of Texas M. D. Anderson Cancer Center
[contact]

Pharmacological assistance

[name], BCNSP,
Clinical Pharmacist Specialist, Pharmacy Clinical Programs,
[name]
John Mendelsohn Faculty Center, FC6.3014
Pharmacy Clinical Programs, The University of Texas M. D. Anderson Cancer Center
Office [name]
[contact]

Clinical Nutrition assistance

[name] BS, MS

Clinical Nutrition Specialist, Clinical Nutrition
[name]
Department of Critical Care, Division of Anesthesiology and Critical Care,
The University of Texas M. D. Anderson Cancer Center
[contact]

[name] BS, MS
Clinical Nutrition Specialist, Clinical Nutrition
[name]
Department of Critical Care, Division of Anesthesiology and Critical Care,
The University of Texas M. D. Anderson Cancer Center
[contact]

Statistical collaborator

[name]
Senior Statistical Analyst, Biostatistics
The University of Texas M. D. Anderson Cancer Center
T. Boone Pickens Academic Tower (FCT4.5005)
[name]
[contact]

SUMMARY TABLE

Title	Early Metabolic Resuscitation: A Potential Solution to Multi-Organ Dysfunction Syndrome in Septic Shock
Question	Is Early Metabolic Resuscitation the Solution to Multi-Organ Dysfunction Syndrome in Patients Diagnosed with Septic Shock?
Protocol Number	2018-0986
Study Size (# of patients)	The sample size will include 112 patients (56 patients randomly assigned to each study group).
Study Design	This is a prospective, single center, un-blinded, randomized controlled trial. Patients will be stratified by type of malignancy, and blocking will be used to ensure balance between study groups. Patients will be randomized to either Early Metabolic Resuscitation with Standard of Care (SC + EMR) or Standard of Care alone (SC). The randomization will be conducted through CORe.
Primary Objective	The primary objective of this study is to assess the efficacy of administering Early Metabolic Resuscitation with Standard of Care (SC + EMR) in patients diagnosed with septic shock for reducing 28-day mortality versus using the Standard of Care alone (SC).

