10.2 Sample Size Justification and Randomization

The rate of 28 day mortality from septic shock at the UT MD Anderson Cancer Center was 70% in 2017. With the objective of decreasing this rate to 40%, a sample size of 112 patients (56 per group) provides 90% power to detect a 30% absolute reduction in the rate of 28 day mortality using a two-sided chi-square test at the 0.05 significance level. We plan to use stratified randomization in a 1:1 fashion to assign patients into two groups, and a fixed block size consisting of 4 patients will be applied for this purpose. The randomization will be conducted in CORe (Figure 2).

Tables 3 displays effect sizes that correspond with conducting a test of equal proportions after randomizing 56 patients to each study arm. The first scenario in Table 3 is what we have currently provided in the protocol. Subsequent scenarios in Table 3 illustrate the change the in the effect size as the Type I error increases. Table 4 is provided to illustrate effect size results if the power is reduced to 80%. Smaller effect sizes are detectable if you increase Type I error or reduce power.

Table 3. Effect size with varying Type I error with Sample Size and Power controlled at 56 patients per study arm and 90%, respectively

Sample Size Per Study Group	Effect Size (percentage point change from $\hat{\pi}_0 = 70\%$)	Type I error
N = 56	-30% (0.70 vs 0.40)	0.05
N = 56	-27% (0.70 vs 0.43)	0.10
N = 56	-25% (0.70 vs 0.45)	0.15
N = 56	-24% (0.70 vs 0.46)	0.20

[figure not shown]
Estimates provided by (nQuery Advisor v7.0) for the difference between two proportions using a two-sided chi-square test.

Table 4. Effect size with varying Type I error with Sample Size and Power controlled at 56 patients per study arm and 80%, respectively

Sample Size Per Study Group	Effect Size (percentage point change from $\hat{\pi}_0 = 70\%$)	Type I error
N = 56	-26% (0.70 vs 0.44)	0.05
N = 56	-23% (0.70 vs 0.47)	0.10
N = 56	-21% (0.70 vs 0.49)	0.15
N = 56	-20% (0.70 vs 0.50)	0.20

Estimates provided by (nQuery Advisor v7.0) for the difference between two proportions using a two-sided chi-square test

Figure 2. Sample size and randomization

[figure not shown]

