10.6 Safety monitoring for Patients assigned to (SC + EMR)

Patient safety will be monitored group sequentially for the first 50 patients in (SC + EMR) group. The monitoring rule will be applied in cohorts of size 10 during the 7 days of treatment.

Patient safety will be monitored to ensure that the rate of select AEs described in Section 8.2 (which include: severe fluid overload, untreatable electrolyte abnormalities, severe hyper/hypoglycemia, allergic reactions) does not exceed 25%. If the AE rate exceeds 25%, then the novel treatment approach of (SC + EMR) exceeds an acceptable rate and the trial will suspend accrual, while at the same time, protecting patients from the burden of being exposed to an untoward therapy.

We will employ Bayesian stopping boundaries derived using a beta-binomial distribution. We will consider the treatment as acceptable if the AE rate during the first seven days post administration of (SC + EMR) is below 25%. The following prior probability for the AE rate will be modeled with a beta distribution (1, 1). Allowing θ_T to denote the true rate of AEs, the trial will suspend accrual if the $\text{Prob}(\theta_T > 0.25 | \text{data}) > 0.80$. Patients will be monitored in cohorts of size 10 according to the following stopping boundaries displayed in Table 3.

Table 4 illustrates the operating characteristics associated with the Bayesian stopping rule. The probability of stopping accrual early is 61% if the true AE rate is 30%.

Table 3. Stopping Boundaries assuming prior $\theta_T \sim \text{beta}(1, 1)$

Number of Patients Evaluated	Recommended stopping accrual if \geq AEs are observed
10	4-10
20	7-20
30	10-30
40	13-40
50	15-50

*stopping boundaries and operating characteristics supplied using

<https://ibl.mdanderson.org/BTM/>

Table 4: Operating Characteristics for the Bayesian Sequential Design

True AE Rate	Probability of Stopping Accrual Early	Average Sample Size
0.1	0.014	49.5
0.2	0.180	43.7
0.3	0.610	29.9
0.4	0.928	17.7
0.5	0.996	12.3

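### The safety-rule operating characteristics in section 10.6 omit stops at the listed fifth boundary (15 of 50), although the EMR arm is planned at 56: counting them, the chance of stopping at a 30% AE rate is about 69%, not 61%

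*Combined protocol and SAP*

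**What the plan says.** Section 10.6 sets the scope of safety monitoring: "Patient safety will be monitored group sequentially for the first 50 patients in (SC + EMR) group". On timing it says: "The monitoring rule will be applied in cohorts of size 10 during the 7 days of treatment". The prior for the AE rate is beta(1, 1), and accrual is suspended when the posterior probability that the rate exceeds 25% is above 0.80.

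The boundary table (Table 3 of section 10.6, not the Table 3 of section 10.2) has five rows: stop at 4 or more AEs in 10, 7 in 20, 10 in 30, 13 in 40 and 15 in 50.

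The operating-characteristics table (Table 4 of section 10.6) is presented as describing this stopping rule. For true AE rates of 0.1, 0.2, 0.3, 0.4 and 0.5 it gives stopping probabilities of 0.014, 0.180, 0.610, 0.928 and 0.996, and average sample sizes of 49.5, 43.7, 29.9, 17.7 and 12.3. The text repeats the middle row: "The probability of stopping accrual early is 61% if the true AE rate is 30" per cent.

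The arm size is fixed in section 10.2: "a sample size of 112 patients (56 per group) provides 90% power".

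**The concern.** The rule has a boundary at 50 patients and the arm has 56. If 15 of the first 50 EMR patients have a qualifying event, accrual is suspended with up to six EMR patients still to enrol. In this trial that is an early stop, so the stated probabilities should include it. Average sample sizes that approach 50 at low AE rates suggest that the table was produced for a design ending at 50.

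This table and sentence are the only figures in the protocol from which a reviewing board can judge how often the rule would suspend the trial, at acceptable rates and at unacceptable ones. They should describe the rule and the arm size that the trial will use.

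**Working it through.** **Inputs (sections 10.2 and 10.6).** Looks at n = 10, 20, 30, 40, 50; boundaries b = 4, 7, 10, 13, 15; prior beta(1, 1); limit 0.25; cutoff 0.80; EMR arm 56.

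**Step 1: are the boundaries right?** With x events in n patients the posterior is beta(1 + x, 1 + n − x). The posterior probability of a rate above 0.25, at the boundary and at one event fewer, is:

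| n | at boundary | one fewer |
|---|---|---|
| 10 | 4: 0.885 | 3: 0.713 |
| 20 | 7: 0.870 | 6: 0.744 |
| 30 | 10: 0.872 | 9: 0.771 |
| 40 | 13: 0.878 | 12: 0.794 |
| 50 | 15: 0.815 | 14: 0.720 |

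All five are the smallest counts that exceed 0.80. The row at 50 is a genuine boundary of the stated rule.

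**Step 2: recursion.** Let f_j(x) be the probability of having x events after look j without an earlier stop, at true rate p. Then f_j(x) = Σ_k f_{j−1}(x − k) · C(10, k) p^k (1 − p)^(10 − k). The stopping probability at look j is s_j = Σ f_j(x) over x ≥ b_j; those paths are then removed. With maximum enrolment M, average enrolment is Σ n_j s_j + M(1 − Σ s_j).

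**Step 3: reproduce the plan's figure.** At p = 0.30 the five values of s_j are 0.35039, 0.13461, 0.07556, 0.04988 and 0.07805.
- Looks 1 to 4 only: 0.35039 + 0.13461 + 0.07556 + 0.04988 = 0.610, the stated value.
- Average with M = 50: 10(0.35039) + 20(0.13461) + 30(0.07556) + 40(0.04988) + 50(0.38957) = 10.458 + 19.479 = 29.9, the stated value.

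The same calculation at the other rates gives 0.014/49.45, 0.180/43.70, 0.928/17.69 and 0.996/12.33. Every cell of the table is matched by four looks and a maximum of 50.

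**Step 4: count the fifth boundary, M = 56.** At p = 0.30, stopping is 0.610 + 0.078 = 0.688. Average enrolment is 10.458 + 50(0.07805) + 56(0.31151) = 31.8.

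| True AE rate | Stop, stated | Stop, five looks | Average N, stated (max 50) | Average N, five looks (max 56) |
|---|---|---|---|---|
| 0.10 | 0.014 | 0.014 | 49.5 | 55.4 |
| 0.20 | 0.180 | 0.195 | 43.7 | 48.5 |
| 0.25 | not shown | 0.425 | not shown | 40.9 |
| 0.30 | 0.610 | 0.688 | 29.9 | 31.8 |
| 0.40 | 0.928 | 0.967 | 17.7 | 17.9 |
| 0.50 | 0.996 | 0.999 | 12.3 | 12.3 |

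**Step 5: why the averages move.** With M = 50, a stop at 50 and completion at 50 both contribute 50 patients, so the fifth look changes no average. With M = 56 and four looks, the average at p = 0.30 is 10.458 + 56(0.38957) = 32.3; adding the fifth look lowers it to 31.8. The increase over the stated averages therefore comes from the larger maximum, not from the omitted look.

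**The case against.** The strongest reply is that nothing was miscalculated. Section 10.6 monitors the first 50 EMR patients, and for a monitored cohort of 50 the table is right in every cell: 0.610 is the probability of stopping before that cohort is complete. This explains where the number comes from, and it shows that the mismatch is one of scope rather than a computing slip. But the protocol nowhere defines an early stop as one before patient 50. It speaks of stopping accrual, accrual to the EMR arm runs to 56, and the table is offered as describing a rule that includes the boundary at 50. On the ordinary reading the 61% is not the figure for this design.

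A second reply is that little depends on it. This largely stands. Decisions are taken from the boundary table, which is correct. A stop at 50 spares at most six EMR patients, possibly fewer, because events are counted over seven days and section 10.6 does not say that accrual pauses while a cohort is evaluated.

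A reader might infer that the rule stops too readily at acceptable rates. The figures do not support that as a material problem: the change is nil to three decimals at 10%, and about 1.5 points at 20% (0.180 to 0.195). The larger differences, 7.8 points at 30% and 3.9 at 40%, lie above the 25% limit, where more stopping means more protection than stated.

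**Conclusion.** The point holds, with minor severity. The operating-characteristics table and the 61% sentence describe a 50-patient arm and leave out stops at the listed boundary of 15 in 50. For the planned arm of 56 the stopping probability at a 30% rate is 0.688, about 69%.

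Two stronger conclusions are not supported. The boundaries are not wrong; all five follow from the stated prior and cutoff. Nor does the omitted look explain the low stated averages, since that difference reflects a maximum of 50 rather than 56.

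The recomputation assumes independent patients with a common AE rate, each counted once as having or not having a qualifying event, looks at exactly 10, 20, 30, 40 and 50 patients, and no enrolment while a cohort is being evaluated. The stated table reproduces exactly under the same assumptions. The average enrolments also ignore any stop from the efficacy interim analysis in section 10.3.

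**What to change.** In section 10.6, replace the operating-characteristics table with the five-look values for a maximum of 56 EMR patients: stopping probabilities 0.014, 0.195, 0.688, 0.967 and 0.999, and average enrolments 55.4, 48.5, 31.8, 17.9 and 12.3. Change the 61% in the text to about 69%, and state under the table that it counts all five boundaries and a 56-patient arm. A row at the 25% limit (0.425) is optional but useful, because that is the rate on which the rule is built.

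Do not delete the boundary at 50 to make the table fit. It follows from the stated posterior rule, and removing it would weaken a safety rule to suit a descriptive table.

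The cost is one table and one sentence. Design, boundaries and conduct are unchanged.

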11.0 DATA COLLECTION AND QUALITY ASSURANCE

11.1 Records to Be Kept

All patient-reported outcomes, laboratory, and clinical data gathered in this protocol will be stored in a password-protected database. A digital data collection form will be used to record data relating to outcomes described (to be included in appendix). All patient information will be handled using anonymous identifiers. Linkage to patient identity is only possible after accessing a password-protected database. Access to the database is only available to individuals directly involved in the study. Information gathered for this study will not be reused or disclosed to any other person or entity, or for other research. Once the research has been completed, identifiers will be retained for as long as is required by law and by institutional regulations, and at that point will be destroyed.

11.2 REDCap Summary

Study data will be collected and managed using REDCap (Research Electronic Data Capture) electronic data capture tools hosted at MD Anderson. REDCap (www.project-redcap.org) is a secure, web-based application with controlled access designed to support data capture for research studies, providing: 1) an intuitive interface for validated data entry; 2) audit trails for tracking data manipulation and export procedures; 3) automated export procedures for seamless downloads to common statistical packages; and 4) procedures for importing data from external sources. In the case of multi-center studies REDCap uses Data Access Groups (DAGs) to ensure that personnel at each institution are blinded to the data from other institutions. REDCap (<https://redcap.mdanderson.org>) is hosted on a secure server by MD Anderson Cancer Center's Department of Research Information Systems & Technology Services. REDCap has undergone a Governance Risk & Compliance Assessment (May 2014) by MD Anderson's Information Security Office and found to be compliant with HIPAA, Texas Administrative Codes 202-203, University of Texas Policy 165, federal regulations outlined in 21CFR Part 11, and UTMDACC Institutional Policy #ADM0335.

Those having access to the data include the study PI and research team personnel. Users are authenticated against MDACC's Active Directory system. External collaborators are given access to the database once approved by the PI, with their access expiring in 6 months but renewable in 6 month increments at the request of the PI. The application is accessed through Secure Socket Layer (SSL). All protected health information (PHI) will be removed from the data when it is exported from REDCap for analysis. All dates for a given patient will be shifted by a randomly generated number between 0 and 364, thus preserving the distance between dates. Dates for each patient will be shifted by a different randomly generated number.

Following publication, study data will be archived in REDCap. Since study data may be useful for future research studies performed under separate IRB approved protocols, study data will be archived indefinitely in REDCap. Since REDCap is a secure electronic database with controlled access, and because patient identifiers may be needed to link study data to data from other sources under future IRB approved protocols, patient identifying information will be retained in the archived database.

11.3 Data Management

The PI will oversee the day-to-day operation of the project along with the Project Coordinator. The PI is responsible for reporting on trial progress to the IRB and he will take responsibility for the conduct of the research team, including, in general, optimal research ethics, adherence to protocol, and commitment to study completion. Specifically, site start-up and maintenance, protocol refinement, assurance of data quality, and trial success are the responsibility of both co-applicants and collaborators.

11.4 Quality Assurance

11.4.1 Training

Prior to the undertaking of the study, several educational sessions will be provided to ICU physicians (faculty and trainees), nurses, and advanced nurse practitioners (where present). These will be provided by the study chair [name] or their designees. These sessions will focus on training ICU staff with the protocol with particular focus on:

- *New definitions of sepsis and septic shock*
- *Rationale and purpose of study*
- *The interventions given*
- *Possible adverse reactions and how to manage them (particular focus on electrolytes & glucose)*
- *Criteria for intervention discontinuation*
- *Study team composition and contact information*
- *Adverse event reporting*

11.4.2 Quality Control

Integrity of data is ensured by oversight from MD Anderson's Data Monitoring and Safety Board. As well as adverse event reporting and annual reports will be provided to the DSMB with the help of the trial statisticians in order to ensure integrity of the data. Along with planned recording for protocol deviations, we feel this will ensure the integrity and quality of the data recorded

11.4.3 Protocol Deviations

Deviations from protocol, whether or not they may lead to harm or risk of harm, will be recorded by investigators and provided to the principle investigator who may share these

with the DSMB. Protocol deviations, if felt to be significant, will be shared with statisticians and included in potential analyses where possible.

11.4.4 Monitoring

Protocol compliance will be assessed by review of records, including inpatient electronic records, by the research team during the collection of study outcomes. All consent documents and any other information collected non-electronically will be reviewed by the principle investigator. The MD Anderson Data and Safety Monitoring Board (DSMB) may decide to audit the research at any stage and review the progress of the research at the frequency they so desire.

12.0 PARTICIPANT RIGHTS AND CONFIDENTIALITY

12.1 Institutional Review Board (IRB) evaluation

This study and any amendments to it are subject to review by the MD Anderson Institutional Review Board before the commencement of any research activities. The MD Anderson IRB is registered with the Office for Human Research Protections and is compliant with all international, national and local guidelines pertaining to the conduct of research using human subjects.

12.2 Informed Consent

A signed IRB approved consent form will be obtained from the subject or, if the subject's lacks decision-making capacity, the subject's legally authorized representative will sign the consent form on their behalf. The consent form describes the purpose of the study, the procedures to be followed, and the risks and benefits of participation. A copy of the consent form will be given to the subject or to the subject's legally authorized representative, and this fact will be documented in the subject's record.

12.3 Subject Confidentiality

Study confidentiality standards will be followed handling the data. No patient identifiable data will be shared outside of the research team. All computer entry for data analysis will be done using study identification numbers only. Clinical information will not be released without written permission of the subject, except as necessary for monitoring by IRB, the FDA, or the OHRP.

12.4 Study Modification/Discontinuation

The study may be modified or discontinued at any time by the IRB, the OHRP, the FDA, or other government agencies as part of their duties to ensure that research subjects are protected.

13.0 PUBLICATION OF RESEARCH FINDINGS

Publication of the results of this trial will be governed by the policies and procedures developed by MD Anderson. Any publications or presentations must be agreed with the co-principle investigators prior to publication.

15. APPENDIX

EMR Glucose Algorithm

[figure not shown]

EMR Potassium Algorithm

EMR Phosphorus Algorithm

Sodium and Albumin Maintenance Fluid Algorithm
